1.2 Purpose

The purpose of the study is to complement the ofatumumab Phase 3 program by exploring outcomes of patients transitioning from any fumarate-based RMS approved therapy, such as dimethyl fumarate (DMF generic or branded) or diroximel fumarate (DRF), or fingolimod (generic or branded) to ofatumumab due to breakthrough disease in a specialized clinical practice and tertiary care settings.

Breakthrough disease has been defined as:

- At least one documented relapse during previous year OR two relapses during previous two years prior to inclusion
- Or presence of at least one Gd+ lesion on an MRI scan within the last 12 months
- Or presence of new or enlarging T2 lesions within the last 12 months

A combination of clinical and/or imaging findings is also accepted for inclusion.

Protocol No. COMB157G23101

The primary outcome will be to demonstrate the treatment effectiveness of ofatumumab in subjects with relapsing forms of MS as measured by ARR at 96 weeks. This Phase IIIb study will provide additional data on patient reported outcomes, biomarker outcomes and explore the utility of digital tools for patient assessments and treatment persistence / adherence.

Exploratory outcomes include assessments of processing speed, daily activity, physical functioning, and patient reported outcomes. Outcomes will be captured digitally and compared to clinical assessments wherever possible. NfL and CCI monitoring during the trial will better elucidate the underlying disease activity during RMS.

2 Objectives and endpoints

Table 2-1 Objectives and related endpoints

Objective(s)	Endpoint(s)		
Primary objective(s)	Endpoint(s) for primary objective(s)		
Demonstrate the effectiveness of ofatumumab 20 mg s.c. administered every 4 weeks in subjects with relapsing forms of MS who had breakthrough disease on fumarates or fingolimod	Annual relapse rate (ARR, based on confirmed relapses) measured over the 96 weeks		
Secondary objective(s)	Endpoint(s) for secondary objective(s)		
 Evaluate the safety of ofatumumab 20 mg s.c. administrated every 4 weeks in subjects with relapsing forms of MS who had breakthrough 	 Proportion of subjects with adverse events, including injection related reactions Proportion of patients with laboratory or vital signs results meeting abnormal criteria 		
disease on fumarates or fingolimod	 The proportion of subjects discontinuing treatment due to insufficient effectiveness (lack of efficacy) or tolerability/safety reasons 		

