5.1 Inclusion criteria

Subjects eligible for inclusion in this study must meet all of the following criteria:

- 1. Written informed consent must be obtained before any assessment is performed.
- 2. Adult subjects aged 18 to 60 years (inclusive) at Screening.
- 3. Diagnosis of MS according to the 2017 Revised McDonald criteria (Thompson et al 2018)
- 4. Relapsing MS: relapsing forms of MS (RMS) including RMS and secondary progressive MS (SPMS) (Lublin et al 2014).
- 5. Disability status at Screening with an EDSS score of 0 to 4 (inclusive).
- 6. MS treatment history with a maximum of 3 DMTs, where all fumarates are considered as one DMT
- 7. Subject transitioning from either any fumarate-based RMS approved therapies, such as dimethyl fumarate (DMF) or diroximel fumarate (DRF), or fingolimod which was administered for a period of at least 6 months, as their last DMT before first study drug administration

- 8. Breakthrough disease activity while the participant was adequately using fumarates or fingolimod prior to transitioning for a minimum of 6 months as evidenced by one or more clinically reported relapses or one or more signs of MRI activity (e.g. Gd+ enhancement, new or enlarging T2 lesions)
- 9. Neurologically stable within one month prior to first study drug administration.

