Sample for B-cell and T-cell subset testing (US sites only)		X				Х			×		Х		X		Х
Serological markers for hepatitis B and C ²⁶	Х														
Syphilis/Tuberculosis Assessment ²⁶	Х														
Pregnancy Test (serum) ²¹	Х										Х				Х

Period	Scre	ening						Tre	atment						
Visit Name	Screening	Baseline	Visit 1 ²	Visit 2 (Remote contact Visit) ³	Visit 3 Week 2 ²⁴	Visit 4 Week 4	Visit 5 Week 8 ²⁴	Visit 6 Week 12 ²⁴	Visit 7 Week 24	Visit 8 Week 36 ²⁴	Visit 9 Week 48	Visit 10 Week 60 ²⁴	Visit 11 Week 72	Visit 12 Week 84 ²⁴	EOS/Visit 13 Week 96 ⁴
Visit Numbers ¹	1	20	100	110	120	130	140	150	160	170	180	190	200	210	220
Days	-60 to -8	-7 to 1 (Prior to 1 st dose/visit 1 start)	1	7 ±1	14 ±1	28 ±1	56 ±7	84 ±7	168 ±14	252 ±14	336 ±14	420 ±14	504 ±14	588 ±14	672 ±14
Urine Pregnancy Test ²¹			X ¹³			Х	Х	Χ	Х	Х	X	Х	Х	Χ	Х
C-SSRS	Х		X ¹³		Х	Х	Х	Х	Х	Х	Х	Х	Х	Х	Х
Contraception Status ^{6,22}	Х	Х	Χ		Х	Х	Х	Χ	Х	Х	Х	Х	Х	Χ	Х
Concomitant medications ²³	Х	Х	Х	Х	Х	Х	Х	Х	Х	Х	Х	Х	Х	Х	Х
Adverse Events	Х	Х	Χ	Х	Х	Х	Х	Χ	Х	Х	Х	Х	Х	Х	Х
Subject Diary Review ⁶			Χ	Х	Χ	Χ	Χ	Χ	Х	Х	Χ	Х	Х	Χ	Х
Subject Disposition															Х

X Assessment to be recorded in the clinical database or received electronically from a vendor

¹ Visit structure given for internal programming purpose only

² Enrollment and first dose (usually expected on the same day). If first dose occurs on a different day after enrollment, the day of the first dose should be considered as Day 1

³ Remote contact visit to support home/self-administration of the study drug, support compliance with the diary and provide additional training as needed. An on-site visit is permitted in case the subject is unable/unwilling to self-administer injections.

⁴ EOS visit will be required for all subjects (subjects who permanently discontinue study drug and subjects who complete the study).

⁵ MS history including number of relapses in previous year and number of relapses in previous two years

⁶ Assessments captured as source data

⁷ At Baseline visit, patient training on CCI and and CCI (as required) CCI s's functionality and use. At day 1 patient training on study requirements including study drug administration using the autoinjector, ePRO, urine pregnancy tests used at home

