A subject may report symptoms indicative of a relapse at a planned visit or at any other time. Subjects will be instructed to immediately contact the Investigator if he/she develops new, reoccurring or worsening neurological symptoms. During each remote contact performed during the study, the subject will also be asked whether any such symptoms have occurred between scheduled visits. If a subject reports new neurological symptoms or worsening of previous symptoms, an unscheduled visit is to be scheduled as soon as possible, preferably within 7 days. During this visit, the Investigator will first assess whether the new/worsening neurological abnormality is consistent with the definition of MS relapse above. If so, the standard neurological examination (for the EDSS score) will be performed by the EDSS Rater. If there is any doubt in the opinion of the Investigator, the default must always be to refer the case to the EDSS Rater to perform an EDSS rating. The EDSS rater should perform the EDSS rating the same day as the subject's visit to the Investigator whenever possible. Later EDSS assessments can still be utilized for confirmation of MS relapses, but should be avoided to reduce the risk of changes in subject status in between the initial assessment by the Investigator and the EDSS rating by the EDSS rater. A blood sample will be collected during this subject's visit to the investigator for NfL and **CCI** sampling.

Confirmation of MS relapse

The definition of a confirmed MS relapse is one accompanied by a clinically relevant change in the EDSS performed by the EDSS Rater, i.e. an increase of at least 0.5 points on the EDSS score, or an increase of 1 point on two functional scores (FSs) or 2 points on one FS, excluding changes involving bowel/bladder or cerebral FS compared to the previous available rating (the last EDSS rating that did not occur during a relapse). Confirmation of MS relapse based on these definitions will be done centrally.

All MS relapses, regardless if they meet definition for confirmation based on EDSS or not, are reported on the appropriate CRF. Severity of MS relapse will be calculated centrally per criteria in Table 8-3 below. MS relapse should not be reported as an AE/SAE unless, in the judgment of the Investigator it is unusually severe or medically unexpected and warrants specific notification as an SAE (as described in Section 10.1.2).

Table 8-3 Severity of MS relapse

Mild Relapse	Moderate Relapse	Severe Relapse

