12.6 Analysis of exploratory endpoints

Exploratory endpoints will be explored/evaluated through the use of visualization/exploration tools and relevant findings will be provided in the CSR. The details of exploratory endpoints analysis will be provided in a separate statistical analysis plan (SAP).

Long term efficacy of ofatumumab:

The following endpoints will be explored for describing the long-term efficacy of ofatumumab 20 mg s.c. once q4 weeks:

- Change from baseline in Expanded Disability Status Scale (EDSS)
- Change from baseline in Time 25-Foot Walk (T25FW)
- Change from baseline in Nine Hole Peg Test (9HPT)
- Change from baseline in **CC**
- Change from baseline in Low Contrast Visual Acuity (LCVA)
- Change from baseline in T2 lesion volume (T2VOL)
- Time to 6-month confirmed Disability Worsening (6mCDW)
- Time to a 6-month confirmed cognitive decline (6mCCD, defined as a 4-point worsening on CCI)
- Number of T1 Gd+ lesions per scan
- Number of new or enlarging T2 lesions on MRI per year (annualized T2 lesion rate)
- Proportions of subjects after 48 and 96 weeks that meet the criteria of No evidence of disease activity three (NEDA-3)

Change from baseline in ARR, EDSS score, T25FW score, 9HPT, CCI, T2VOL and LCVA will be summarized descriptively by visits. Adjusted estimates will be obtained using repeated measures models.

Time to 6mCDW, Time to 6-month confirmed 4-point worsening on CCI will be analyzed by Kaplan-Meier (KM) method. KM curve and KM estimates at each year will be presented.

Number of T1 Gd+ lesions and number of new or enlarging T2 lesions for the entire duration will be summarized descriptively. The proportion of patients with/without MRI lesion activity will also be summarized descriptively.

Proportions of subjects after 48 and 96 weeks that meet the criteria of No evidence of disease activity three (NEDA-3) will be summarized descriptively.

FAS will be used as analysis set for the analysis of all efficacy endpoints.

Biomarker:

The following endpoints will be explored related to biomarker for MS:

- Change from baseline serum Neurofilament (NfL) concentration
- Relationship between baseline serum NfL and disease activity, disease course, treatment response
- Utility of NfL for disease activity monitoring
- Change from baseline serum **CCI** concentration
- Relationship between baseline serum **CCI** and disease activity, disease progression and treatment response

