2.3.3 MS baseline disease characteristics

MS baseline characteristics, MS disease history and MS medication history will be summarized for the FAS. MS baseline characteristics include baseline EDSS, 9HPT, T25FW, CCL LCVA, key MRI parameters (e.g., number of Gd-enhancing T1 lesions, number of T2 lesions, T2 lesion volume), Biomarkers such as NfL and IgG, IgM, CD-19 B-cell counts, Lymphocytes and neutrophils.

Baseline lymphocyte and neutrophil values should also be summarized, including reporting of lymphocyte and neutrophil abnormalities (Table 2-12).

Of note, laboratory values below limit of quantification (e.g. value coded as <x.xx) will be imputed to the lower limit of quantification/2. MS baseline disease characteristics will also be summarized by last prior DMT.

Table 2-12 Notable abnormalities for lymphocyte and neutrophil counts

Lymphocytes (10E9 /mL)	Decrease in lymphocytes counts: Gr1: <lln -="" 0.2="" 0.5="" 0.8="" 10e9="" <0.5="" <0.8="" gr2:="" gr3:="" l="" l<="" th="" x=""></lln>
	Gr4: <0.2 x 10E9/L Increase in lymphocytes counts: >4.0 - 20 x 10E9 /L (grade 2 lymphocytosis) >20 x 10E9 /L (grade 3 lymphocytosis)
Neutrophils (10E9 /mL)	Decrease in neutrophils counts: Gr1: <lln -="" 0.5="" 1.0="" 1.5="" 10e9="" <0.5="" <1.0="" <1.5-="" gr2:="" gr3:="" gr4:="" l="" l<="" td="" x=""></lln>

MS disease history includes duration of MS since diagnosis (years), duration of MS since first symptom (years), number of relapses in the last 12 months prior to screening, number of relapses in the 12 to 24 months prior to screening, type of MS at study entry (i.e., RRMS or SPMS), time since onset of SPMS, time since onset of most recent relapse (months), and number of prior DMTs.

Duration of MS since diagnosis (years) will be derived [(first dose date – MS diagnosis start date + 1)/365.25]; duration of MS since first symptom (years) will be derived as [(first dose date – first MS symptom date +1)/365.25]; time since onset of SPMS (years) will be derived as [(first dose date – conversion to SPMS date +1)/365.25]; and time since onset of most recent relapse (months) will be derived as [(first dose date – most recent relapse onset date + 1)/(365.25/12)]. In these calculations, partial dates if any will be imputed according to the rules specified in Section 5.1.4.1.

MS medication history of previous disease-modifying drugs (coded by WHO drug dictionary) will be summarized by preferred term (PT).

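### Protocol 12.6 still lists a change from baseline in ARR, although baseline ARR is undefined and the available before/after contrast is biased towards a fall

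*Protocol*

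**What the plan says.** Protocol 12.6 opens its sentence on change from baseline with "Change from baseline in ARR, EDSS score, T25FW score, 9HPT". It says of the listed variables that they "will be summarized descriptively by visits. Adjusted estimates will be obtained using repeated measures models". ARR is not in the bullet list above that sentence, nor among the readable exploratory endpoints in protocol Table 2-1 or SAP Table 1-1. Readable SAP 2.14 has no such analysis. SAP 2.5.2 gives adjusted, time-based and subject-based on-study ARR, with no contrast against the pre-study period. SAP section 1 does say that data are analysed according to section 12 of the protocol. The list of changes in SAP section 4 is redacted.

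On relapses before the study, Table 8-1 footnote 5 specifies "MS history including number of relapses in previous year and number of relapses in previous two years", and SAP 2.3.3 lists "number of relapses in the last 12 months prior to screening" under disease history. Neither requires an EDSS examination.

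On entry, inclusion criterion 8 accepts "one or more clinically reported relapses or one or more signs of MRI activity". Protocol 1.2 gives as one form of breakthrough disease "At least one documented relapse during previous year OR two relapses during previous two years prior to inclusion".

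On study, protocol 8.3.1 states: "The definition of a confirmed MS relapse is one accompanied by a clinically relevant change in the EDSS performed by the EDSS Rater". Confirmation is central. Only confirmed relapses from first dose onward enter ARR (protocol 12.4.1, SAP 2.5.1).

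**The concern.** The two periods are not measured alike. The history count includes relapses as reported, while the on-study count keeps only the subset that meets an EDSS or functional-score threshold. The history count is also partly selected: subjects who qualified on a relapse have at least one by definition, so their later counts are expected to drift down even if nothing changes. Both effects push the mean in the same direction.

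The study has no comparator arm, so a before/after drop in ARR could easily be taken for a treatment effect if it were reported. The method named also does not suit the variable: ARR is a rate over an interval and has no value at a visit, so a by-visit change and a repeated-measures model have no clear meaning for it.

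**Working it through.** The plan states no baseline ARR and no expected change, so there is no planned figure to reproduce. The check asks what the contrast would show with **no treatment effect and equal ascertainment**.

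**Inputs.** From the documents: relapse or MRI activity as entry routes, an unconfirmed history count, and a confirmed on-study count. Assumed, because the documents give no values:

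- m: mean relapse rate in the source population, 0.2-0.6 per year
- k: gamma-Poisson dispersion, 0.5-1
- q: probability of entering on MRI activity when there was no relapse in the prior year, 0.25-0.5
- c: share of on-study relapses that are confirmed, 0.6-0.9

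Entry on relapse is simplified to at least one in the prior year; the two-in-two-years route is not modelled.

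**Formulas.**

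- Probability of no prior-year relapse: P0 = (1+km)^(-1/k)
- Share enrolled: E = 1 - P0 + q·P0
- Baseline ARR: B = m/E
- True rate of the enrolled: T = (m - L0 + q·L0)/E, with L0 = m(1+km)^(-1/k-1)
- On-study ARR: c·T
- Ratio of on-study to baseline: c·T/B = c[1 - (1-q)(1+km)^(-1/k-1)]

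**Example: m = 0.4, k = 1, q = 0.5, c = 0.8.** P0 = 1/1.4 = 0.714, E = 0.286 + 0.357 = 0.643, L0 = 0.4/1.96 = 0.204.

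| Entry route | Share of enrolled | Baseline | True rate | On-study (×0.8) |
|---|---|---|---|---|
| Relapse | 0.286/0.643 = 0.44 | 0.4/0.286 = 1.40 | (0.400-0.204)/0.286 = 0.69 | 0.55 |
| MRI only | 0.357/0.643 = 0.56 | 0 | 0.204/0.714 = 0.29 | 0.23 |
| All | 1 | 0.4/0.643 = 0.62 | 0.46 | 0.37 |

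The overall ratio is 0.8 × (1 - 0.5/1.96) = 0.8 × 0.745 = 0.60, a 40% fall with no drug effect. The relapse route falls from 1.40 to 0.55; the MRI-only route rises from 0 to 0.23.

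**Over the assumed ranges.**

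- Confirmation rule alone (q = 1, so no selection): ratio 0.60-0.90, a fall of 10-40%.
- Entry selection alone (c = 1): ratio 0.44-0.81, a fall of 19-56%.
- Both: ratio 0.26-0.72, a fall of 28-74%.

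**Offset by ascertainment.** If the study detects relapses better than history does by a factor a, the ratio is multiplied roughly by a. Cancelling the fall in the example needs a = 1/0.60, about 1.7; cancelling the confirmation rule alone needs 1/0.90 to 1/0.60, about 1.1 to 1.7.

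**Using all reported relapses.** Setting c = 1 in the example gives a ratio of 0.745. That removes the definition mismatch but leaves a fall of about 25% from selection.

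**The case against.** The strongest reply is that this is a stray word, already superseded. ARR is missing from the bullets and endpoint tables, the by-visit method does not fit it, protocol 12.6 defers detail to the SAP, and readable SAP 2.14 leaves it out. That makes it quite possible that the analysis will never be run. It does not settle the matter: the operative protocol sentence stands, SAP section 1 refers back to protocol section 12, and a withdrawal in redacted section 4 can be neither confirmed nor excluded.

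A reader might infer that ARR must fall by construction. The documents do not support that. Subjects with no prior-year relapse cannot fall, protocol 6.6.1 acknowledges possible rebound on switching, and monthly contacts with prompt unscheduled visits (8.1.2, 8.3.1) may find relapses that retrospective history would miss. What can be claimed is an expected downward bias in the mean, under stated conditions.

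A reader might also infer that MS history is the sole relapse information before treatment. It is not: Table 8-1 schedules relapse assessment at Screening and Baseline, and footnote 27 applies section 8.3.1 after consent. That window lasts at most 60 days, so it does not supply a baseline year. Taking history as the source of baseline ARR remains an inference.

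Finally, every numerical input above is assumed. That stands in full.

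**Conclusion.** The point holds as a low-priority correction. Protocol 12.6 names an analysis whose baseline is undefined in the readable text. The pre-consent counts available for it are unconfirmed and partly entry-qualifying, whereas the on-study measure is EDSS-confirmed. At an unchanged true rate and equal ascertainment, mean ARR is expected to fall: by 28-74% over the assumed ranges, by 40% in the worked example. The direction rests on confirmed relapses being a subset of reported ones and on selection at entry. The size rests wholly on the assumed rate, dispersion, entry mix and confirmation share, and better on-study detection could offset part of it.

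It would be wrong to read this as a flaw in the primary analysis. That tests on-study confirmed ARR against a fixed 0.18 and uses the prior-year count only as a covariate.

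**What to change.** State in SAP section 4 that change from baseline in ARR is not analysed, or confirm this if it is already listed there. Remove ARR from the sentence in protocol 12.6 at the next amendment; because protocol 14.1 requires formal approval, this does not justify an amendment of its own.

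If a before/after figure is kept:

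- Define baseline ARR: source, window and denominator.
- Count all reported on-study relapses, confirmed or not. Protocol 8.3.1 already has them recorded, and the SAP change log for amendment 4 adds an all-relapse sensitivity analysis.
- Show it separately for subjects who entered on a relapse and those who entered on MRI activity only.
- Drop the by-visit repeated-measures estimate.
- Label it descriptive and subject to regression to the mean, since the all-relapse count does not remove selection.

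No new data are needed. The cost is a sentence in the SAP and the loss, or a less favourable version, of one exploratory figure.

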2.14 Other Exploratory analyses

Following exploratory endpoints will be analyzed as part of CSR based on FAS population.

2.14.1 6-month Confirmed Disability Worsening (6mCDW)

A 6-month confirmed disability worsening (6mCDW) is defined as an increase from baseline in EDSS sustained for at least 6 months. This means that after a scheduled or unscheduled visit at which the participant fulfills the disability worsening criterion as defined in Table 2-16, all EDSS assessments (scheduled or unscheduled) need to also fulfill the worsening criteria until the worsening ("the event") can be confirmed at the first scheduled visit that occurs in the absence of (confirmed or unconfirmed) relapse 6 months/166 days after the onset of the worsening, or later.

In the time to event (6mCDW) analysis, time will be calculated as (the date of EDSS assessment at onset of the event – date of first administration of study drug+1) for patients with the events. Censoring occurs in those participants who did not experience an event up to the analysis cutoff date (i.e. end of treatment epoch date), this includes participants who had a "tentative" disability worsening that could not be confirmed due to an early discontinuation or any another reason.

The censoring time is calculated as (the date of last EDSS assessment up to analysis cutoff date – date of first administration of study drug+1). Additional details are provided in footnote of Table 2-16.

Table 2-16 Criterion for disability worsening based on change in EDSS score

Total EDSS at baseline*	"Disability worsening" criterion
0	≥ +1.5
0.5 to 5	≥ +1
≥5.5	≥ +0.5

A 6-month confirmed disability worsening can have an onset at any scheduled or unscheduled visit if the disability worsening criterion is met. A disability worsening event can only be confirmed at a scheduled visit in the absence of (confirmed or unconfirmed) relapse if, over a period of 6 months (≥166 days=6*30-14 [visit window]) time interval, all assessments meet the worsening criterion.

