If a participant dies due to MS (EDSS=10 at any time), it will be considered a confirmed disability worsening regardless of the baseline EDSS or the change in EDSS. The time will be calculated as (date of EDSS assessment at a tentative onset of the event – date of first administration of study drug+1) or (date of death – date of first administration of study drug + 1) if a tentative onset date does not exist. Note: Death for other reasons than MS (i.e. not EDSS=10) will not be considered a disability worsening.

*Baseline EDSS is defined as the last EDSS assessment prior to the first dose of study medication (protocol inclusion criterion is EDSS 0-4 at screening)

For statistical analysis, Kaplan-Meier curves (and/or cumulative incidence plots) will be provided to present the time-dependent cumulative probability of participants reaching 6mCDW. Kaplan-Meier (KM) estimates will be calculated for the study with 95% confidence intervals. Separate Kaplan-Meier curves and estimates will also be calculated with 95% confidence intervals for last prior DMT subgroup (fumarates vs. fingolimod).

2.14.2 6-month Confirmed Cognitive Decline (6mCCD)

A 6-month confirmed cognitive decline (6mCCD) is defined as at least a 4-point worsening on score sustained for at least 6 months. Event rate by time interval (0-12 months, 12-24 months) will be provided to participants reaching 6mCCD. Cumulative event rate will be calculated with 95% confidence intervals.

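### Year 2 Kaplan-Meier estimate of 6-month confirmed disability worsening: onsets after about Day 520 cannot be confirmed, so a value read at Week 96 is too low

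*Protocol*

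**What the plan says.** Protocol 12.6 plans a Kaplan-Meier analysis of time to 6mCDW: "KM curve and KM estimates at each year will be presented". SAP 2.14.1 and the text under its Table 2-16 set the rules:

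- **Estimates:** "Kaplan-Meier (KM) estimates will be calculated for the study with 95% confidence intervals". No time points are named, so the protocol's yearly points are not replaced.
- **Where confirmation can occur:** "A disability worsening event can only be confirmed at a scheduled visit in the absence of (confirmed or unconfirmed) relapse".
- **How long the worsening must last:** "over a period of 6 months (≥166 days=6*30-14 [visit window]) time interval, all assessments meet the worsening criterion".
- **Cutoff:** a subject is censored if no event has occurred "up to the analysis cutoff date (i.e. end of treatment epoch date"). This includes worsening that was seen but never confirmed.
- **Censoring time:** "The censoring time is calculated as (the date of last EDSS assessment up to analysis cutoff date", less the first dose date, plus one day).

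Protocol Table 8-1 schedules on-treatment EDSS at Weeks 24, 48, 72 and 96, each ±14 days.

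Two other yearly summaries are related. SAP 2.14.7 summarises each NEDA-3 component, including 6mCDW, by year with a split at Day 365.25. For 6-month confirmed cognitive decline (6mCCD), SAP 2.14.2 says "Event rate by time interval (0-12 months, 12-24 months) will be provided" and describes no Kaplan-Meier estimate.

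**The concern.** An event needs two visits: one where worsening is first seen and a later one that confirms it. The event is dated at the first. A subject who first worsens late in the treatment period has no later on-treatment visit to confirm it, so cannot be an event. The same subject, and every event-free completer, still counts in the risk set up to the Week 96 EDSS. The last stretch of the curve thus has a full denominator and no possible numerator, apart from death due to MS, which the SAP counts without confirmation.

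A Year 2 percentage would be read as a 2-year risk of disability worsening. The study has one arm, so no control curve shares the artefact and the absolute percentage is the result. Protocol 12.6 lists the endpoint under long-term efficacy. A flat tail, or a second year with about half the events of the first, could be taken for a treatment benefit that grows with time.

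**Working it through.** **Inputs from the documents.** The SAP's confirmation interval reproduces: 6 × 30 − 14 = 166 days. Week 96 is 96 × 7 = Day 672, with a protocol window of Day 658 to 686. Week 72 is Day 504, with a window of Day 490 to 518. SAP Table 2-3 maps EDSS to Week 96 up to Day 762. With the SAP's 365.25-day year, Year 2 ends at Day 730.5.

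**Assumed inputs.** The documents give no 6mCDW rate for this population. I take a constant hazard of 5% per year (3% and 8% as a range), worsening that persists, and no dropout.

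**Step 1: latest confirmable onset.** This is the last EDSS day minus 166.

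- Week 96 on target: 672 − 166 = Day 506.
- Last day of the protocol window: 686 − 166 = Day 520.
- Last day of the SAP window: 762 − 166 = Day 596, for a visit well outside the protocol window.

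For scheduled visits the last usable onset is therefore Week 72.

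**Step 2: the end of the curve.** Event-free completers are censored at their Week 96 EDSS. Between about Day 520 and that visit there are subjects at risk but no confirmable events, so the estimate does not move. Day 686 is 730.5 − 686 = 44.5 days short of Year 2, so with on-schedule visits nobody is at risk at Day 730.5.

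**Step 3: size with visits on target.** The true risk by day d is 1 − exp(−h × d / 365.25).

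| Hazard per year | Day 336 | Day 504 | Day 672 | Day 730.5 |
|---|---|---|---|---|
| 3% | 2.7% | 4.1% | 5.4% | 5.8% |
| 5% | 4.5% | 6.7% | 8.8% | 9.5% |
| 8% | 7.1% | 10.5% | 13.7% | 14.8% |

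Without dropout, the estimate read at Week 96 equals the Day 504 column. At 5% that is 6.7% against 8.8%, a ratio of 0.76, or 24% low. The ratio is also about 0.76 at 3% and at 8%.

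**Step 4: size with real visit timing.** The Week 72 to Week 96 gap is 672 − 504 = 168 days, only 2 days more than the rule needs. If both visits fall independently and uniformly within ±14 days, 490 of the 841 day pairs (58%) are at least 166 days apart. The estimate is then about 4.5% + 0.58 × (6.7% − 4.5%) = 5.8%. Against 8.8% the ratio is 0.66, so about a third low. Simulation agrees (5.7% to 5.8%). With N = 555 the standard error is about 1.1 points, and the shortfall is 2.1 points on target and 3.0 points with jitter.

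**Step 5: dropout.** In a separate simulation with an assumed 2-year risk of 10% (9.2% at Week 96), 15% dropout moved the estimate from 7.0% to 6.7% on target, and from 6.0% to 5.9% with ±14-day visits. Dropout adds little.

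**Step 6: by-year reading.** At 5% with visits on target, Year 1 shows 4.5% and Year 2 shows (6.7 − 4.5) / (1 − 0.045) = 2.3% of those remaining. A constant risk appears to halve, because Year 1 has two confirmable onset visits and Year 2 has one.

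**The case against.** The strongest reply is that the SAP, not the protocol sentence, governs the analysis. Protocol 12.6 defers detail to the SAP, and SAP 2.14.1 names no yearly points for 6mCDW. The SAP's list of changes to protocol analyses is not visible, so it cannot be known whether the yearly points were dropped. That is fair, but the visible SAP text puts no other time points in their place, and SAP 2.14.7 still reports 6mCDW by year.

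Three stronger readings are tempting, and the documents do not support them.

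- **Nobody is followed to Year 2.** Protocol Table 8-2 schedules EDSS at 3 and 6 months after the EOS visit for subjects who enter Safety Follow-up, and SAP Table 2-3 accepts a Week 96 EDSS up to Day 762. It is the cutoff at the end of the treatment epoch that leaves the Safety Follow-up data out.
- **The Year 2 figure is about 29% too low.** That compares 6.7% with the 9.5% risk at Day 730.5, where with on-schedule visits there is no estimate to be low unless the last value is carried forward. At Week 96, which completers do reach, the on-target shortfall is 24%.
- **The 12-24 month 6mCCD rate suffers by a known amount.** SAP 2.14.2 asks only for worsening sustained for at least 6 months. It states no 166-day rule, and the test's schedule is redacted. The same limit may apply, but it cannot be sized.

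It is also true that the endpoint is exploratory, that no 6mCDW hypothesis is tested, and that the SAP openly says unconfirmed worsening is censored. This limits the weight of the point but does not correct the figure.

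**Conclusion.** The point stands for 6mCDW. With visits inside the protocol windows, no onset after Day 520 (Day 506 on target) can be confirmed before the cutoff, and the curve is flat by rule from about Week 72. A Year 2 estimate taken at Week 96 is at best a Week 72 estimate: about 24% low with visits on target and about a third low with ±14-day timing. These sizes assume a constant 5% annual hazard, persistent worsening and no dropout; the on-target ratio barely changes between 3% and 8%. Taken at Day 730, the estimate does not exist for subjects seen on schedule. The day limits follow from the documents alone, while the percentages rest on the assumptions. The primary annualised relapse rate test is not touched.

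**What to change.** - In Protocol 12.6 and SAP 2.14.1, replace the yearly points with Kaplan-Meier estimates at Week 48 and at the end of the Week 72 visit window (Day 518), with numbers at risk, and drop the Year 2 estimate.
- End the curve at Day 520, or mark that day as the limit of confirmable onset.
- State that the Week 72 value is itself a lower bound, because the gap to Week 96 leaves only 2 days over the 166-day rule.
- Do not instead censor event-free subjects at their last confirmable visit on exact days. They would leave the risk set day by day across the visit window while events are still being counted. In simulation at 5% per year with jittered visits this gave about 14 to 16% at Week 72, against a true 6.7%.
- Put the same caveat on 6mCDW by year in SAP 2.14.7, and on the 12-24 month 6mCCD rate if the same confirmation rule applies there.
- State whether a Safety Follow-up EDSS may confirm an onset.

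The cost is a change of wording in the protocol and SAP and relabelled outputs; no new data are needed. The downside is that no 2-year figure can be quoted.
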